****NOTE: Aim 2 is registered on clinicaltrials.gov as NCT05111548****

2.2 Study Outcome Measures

Aim 1: Determine the feasibility and acceptability of delivering a combined neuromodulation (tDCS) plus cognitive training intervention to outpatients with SMI.

Primary outcome: Participant retention, defined as the percentage of enrolled participants who complete the combined intervention.

Secondary outcome: Self-reported treatment satisfaction, as measured on a 1-10 scale at study completion.

Aim 2: Collect pilot data on the efficacy of the combined intervention, comparing neurocognitive performance following combined treatment to performance after cognitive training alone.

Primary outcome: change in working memory performance

Secondary outcome: change in non-working memory comparison measures

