3.4 Schematic

Aim 1.

	Week 0	Weeks 1-4	End of Week 4	Weeks 5-8	Week 8
Group A (6 participants)	Baseline assessment	tDCS + BrainHQ	Mid-point assessment	BrainHQ	Post-treatment assessment
Group B (6 participants)		BrainHQ		tDCS + BrainHQ	

Aim 2.

	Week 0	Weeks 1-4	End of Week 4	Weeks 5-8	Week 8
Group A (15 participants)	Baseline assessment	Active tDCS + BrainHQ	Post-treatment assessment	No contact	Follow-up assessment
Group B (15 participants)		Sham tDCS + BrainHQ			

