5.2.3 Stopping Rules

In the event that a participant reports discomfort during the tDCS procedure, stimulation will be paused and additional saline/gel will be added to improve the contact, or the current will be incrementally reduced. The session will be discontinued if the patient reports continued discomfort. Immediately after each stimulation session ends, participants will complete a tDCS side effects questionnaire. A study team member will review the responses and will immediately consult the PI if a participant reports a moderate-severe rating for any of the side effects. Those participants, if any, will be given the option of withdrawing from the study. The PI will also withdraw participants if the nature of the side effect is unusual (i.e., not listed as a common side effect) or concerning (e.g., significant acute mood change). Clinically trained study staff will monitor participants closely for mood changes and/or any emergence of suicidal ideation throughout the duration of participation. Participants will be withdrawn in the event of significant symptomatic worsening, including:

1. Current mania: YMRS change of ≥ 7 points at mid-point assessment or clinical observation indicating current mania
2. Worsening of depressive symptoms: 25% increase (i.e., greater severity) in HAM-D total score at mid-point assessment
3. Worsening of psychosis: 25% increase (i.e., greater severity) in PANSS positive total score at mid-point assessment
4. Suicide risk evaluated by a clinician to be high and imminent (e.g., current suicide plan and intent)

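### Three withdrawal thresholds in section 5.2.3 are read at a mid-point visit that the Aim 2 schedule does not contain, so they cannot be applied as written to its 30 participants

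*Combined protocol and SAP*

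**What the plan says.** Section 5.2.3 introduces its list of symptom criteria with "Participants will be withdrawn in the event of significant symptomatic worsening, including" and then gives four items.

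- **Mania:** a YMRS change of at least 7 "points at mid-point assessment or clinical observation indicating current mania".
- **Depression:** "Worsening of depressive symptoms: 25% increase (i.e., greater severity) in HAM-D total score at mid-point assessment".
- **Psychosis:** "Worsening of psychosis: 25% increase (i.e., greater severity) in PANSS positive total score at mid-point assessment".
- **Suicide risk:** a clinician's judgement, tied to no visit.

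The same section also has staff watch for mood change throughout participation, and it adds a side-effect route: "The PI will also withdraw participants if the nature of the side effect is unusual" or concerning, with acute mood change as an example.

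Section 3.4 gives one schematic per aim. The Aim 1 crossover has a "Mid-point assessment" at the end of Week 4. The Aim 2 schematic has a post-treatment assessment in that slot, then a month without contact, then follow-up. Section 5.5 lists three time points (baseline, post-treatment, follow-up), and section 5.4 lists the latter two as the visits after baseline. HAM-D, YMRS and PANSS are given at all three. A note just before section 2.2 says that "Aim 2 is registered on clinicaltrials.gov as NCT05111548"; Aim 1 has its own registration number.

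**The concern.** A mandatory withdrawal rule needs a visit at which its scores are taken. Three of the four listed items name a visit that belongs to the Aim 1 crossover and is absent from Aim 2. Section 5.2.3 is not limited to Aim 1, and section 5.2.1 just before it describes active and sham stimulation, of which sham appears only in the Aim 2 schematic. Staff running Aim 2 would therefore take 5.2.3 as their rule.

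The rule would then be applied inconsistently. Staff would have to settle for themselves what mid-point means, and depressive or psychotic worsening during the course would be handled by judgement rather than by the written cut-offs. Section 11.3.3 adds to this, because it ties prompt notification of the PI and planning for emergency evaluation to worsening as set out in 5.2.3.

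There is also a data consequence. If the thresholds are scored at the post-treatment visit, a participant who meets one is withdrawn after finishing treatment. The only scheduled assessment that this can remove is the one-month follow-up, and section 4.4.3 leaves use of a withdrawn participant's data to the investigator's discretion.

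**Working it through.** This is a cross-check of schedules with simple counts. The plan gives no figure of its own for this point beyond the planned numbers, which reproduce.

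**Planned numbers** (protocol summary, sections 3.1, 3.3 and 3.4)
- Aim 1: 6 + 6 = 12
- Aim 2: 15 + 15 = 30
- Total: 12 + 30 = 42, as section 3.3 states

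**Where a mid-point visit appears.** In the text available the term occurs four times: once in the Aim 1 schematic and three times in 5.2.3. It does not occur in 5.4 or 5.5.

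| | Aim 1 (3.4) | Aim 2 (3.4) | Sections 5.4 and 5.5 |
|---|---|---|---|
| Week 0 | Baseline | Baseline | Baseline (5.5) |
| End of Week 4 | Mid-point | Post-treatment | Post-treatment |
| Week 8 | Post-treatment | Follow-up | Follow-up |

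**Participants with no mid-point visit**
- Share of Aim 2: 30/30 = 100%
- Share of all planned participants: 30/42 = 71%

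**The four criteria in Aim 2, as written**
- Criteria using a mid-point score: 3 of 4
- Of these, with another route inside the item: 1 (mania, by clinical observation)
- Resting on the mid-point score alone: 3 − 1 = 2 (depression, psychosis)
- Applying in full: 1 (suicide risk)

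**If mid-point means End of Week 4.** In Aim 2 this is the post-treatment visit, which section 5.4 places at the conclusion of treatment. On the nominal schedule:
- Sessions remaining once the thresholds are scored: 10 − 10 = 0
- Assessments remaining: 3 − 2 = 1 (follow-up)
- Scheduled HAM-D, YMRS or PANSS ratings between the first and last session: 0

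**Aim 1 for comparison.** The mid-point visit exists and falls at the changeover, after Group A's stimulation block and before Group B's. That the three scales are given there is implied only by 5.2.3, because 5.4 and 5.5 list neither the visit nor its content.

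**Rater time if a reading were added.** Section 5.5 gives 15–30 minutes for HAM-D, YMRS and PANSS.
- 30 × 15 min = 450 min = 7.5 h
- 30 × 30 min = 900 min = 15 h

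This assumes that the row covers the three scales together. With that reading a post-treatment visit takes at most 30 + 30 + 5 + 10 = 75 min, within the stated 1.5 h (90 min). At 30 min per scale it would take 90 + 30 + 5 + 10 = 135 min, which does not fit.

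**The case against.** The strongest reply is that the problem is only a label. Both schematics have the same columns, End of Week 4 is the middle of three assessments in each aim, and the three scales are scheduled at the Aim 2 visit in that slot. On that reading all 30 participants do have a reading point. This is a possible reading, but the plan does not state it. It also gives a rule that sits under tDCS treatment visits and yet, in Aim 2, is scored once stimulation is over.

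A second reply is that Aim 1 is little different. At its mid-point Group A has finished tDCS and Group B has not begun, so no scheduled reading falls inside anyone's stimulation block, and only the 6 participants in Group B still have stimulation ahead. That is correct, and it means the intended role of the thresholds needs stating for both aims. It does not supply the missing visit in Aim 2.

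A third reply is that other safeguards remain. The list is open-ended. Section 4.4.2 lets the investigator withdraw anyone at unacceptable risk, section 6.1.3 requires adverse-event questions at every treatment session, and section 7.0 provides for roughly weekly investigator meetings. Section 5.2.4 asks for the final-visit assessments at early termination if the participant is willing and able, which softens the loss of data but does not replace the one-month time point. All of this stands and limits the consequence. None of it gives the three thresholds a reading point during Aim 2 treatment.

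Two smaller points also stand. Section 6.2 keeps participants who complete fewer than ten sessions and allows a 10-day window around the post-treatment visit, so the count of zero remaining sessions holds for the nominal schedule only. The summary calls the 30 completers while section 1.0 speaks of 30 enrolled. If dropouts are replaced, 30 and the rater hours are lower bounds.

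**Conclusion.** The concern holds and should be fixed. It is an internal inconsistency about a visit and implies nothing about the clinical content of the rule. As written, three of the four listed withdrawal criteria depend on a visit that none of the 30 planned Aim 2 participants has. The mania item can still act through clinical observation; the depression and psychosis items have no other route within the list. Under the End of Week 4 reading the thresholds can be scored, but on the nominal schedule only after the last session. The finding rests on section 5.2.3 applying to both aims, as its text and setting indicate, and on the schedules in 3.4, 5.4 and 5.5 being complete. It does not mean that worsening in Aim 2 would go unmonitored.

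**What to change.** Reconcile section 5.2.3 with sections 3.4, 5.4 and 5.5 so that each score-based criterion names an assessment that exists on each aim's schedule, and state whether the criterion is meant to act during the stimulation course. If the Aim 1 mid-point visit stays as a reading point, add it and its scales to 5.4 and 5.5. Which thresholds and timings are right is for the investigators, and none is proposed here.

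If the criteria are tied to existing visits, the cost is a wording amendment to 5.2.3 and an added entry in 5.4 and 5.5. If the investigators intend them to act during stimulation, the schedules in 3.4, 5.4 and 5.5 would have to change as well, at about 7.5–15 rater hours over 30 Aim 2 participants for each added reading. Neither course changes the sample size or the randomization.

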4.2 Exclusion Criteria

(1) history of neurological illness or brain injury (e.g., stroke), (2) history of loss of consciousness > 20 minutes, (3) diagnosed intellectual disability, (4) current (i.e., past 30 days) substance use disorder, (5) current mania (YMRS \geq 10) or moderate depression (HAM-D \geq 17) or severe psychosis (PANSS positive symptom total \geq 35), (6) serious suicidal ideation/behavior (endorse questions 4 or 5 or suicide behaviors within the past 3 months, according to the C-SSRS), (7) pregnant or trying to become pregnant, or currently lactating, (8) presence of metal (except titanium) or electrical implants in the brain or skull (e.g., surgical clips, deep brain stimulator, cochlear implants, splinters/fragments, skull plate), (9) presence of implanted medical devices elsewhere in the body (e.g., cardiac pacemaker or medical pump).

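### The score-based withdrawal rules in 5.2.3 are not workable as written: current mania has two definitions, the HAM-D percentage rule fails at low baselines, and Aim 2 has no mid-point visit

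*Combined protocol and SAP*

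**What the plan says.** Section 4.2 excludes on absolute scores: "current mania (YMRS \geq 10", "moderate depression (HAM-D \geq 17" and "severe psychosis (PANSS positive symptom total \geq 35" (that is, scores of 10, 17 and 35 or more). It sets no lower limit on any scale.

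Section 5.2.3 makes withdrawal mandatory for significant symptomatic worsening and lists four cases. Three of them use scores:

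- "Current mania: YMRS change of ≥ 7 points at mid-point assessment or clinical observation indicating current mania"
- for depression, a "25% increase (i.e., greater severity) in HAM-D total score at mid-point assessment"
- for psychosis, a "25% increase (i.e., greater severity) in PANSS positive total score at mid-point assessment"

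The fourth is a clinician's judgement of suicide risk. No reference score is named (presumably baseline), and no minimum point change or absolute level is set for the two percentage rules.

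On timing, the schematic in 3.4 shows a mid-point assessment at the end of Week 4 for Aim 1 only. In the Aim 2 schematic the visit in that position is the post-treatment assessment. Sections 5.4 and 5.5 schedule HAM-D, YMRS and PANSS at baseline, post-treatment and follow-up, and mention no mid-point.

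The Aim 1 primary outcome in 2.2 is "Participant retention, defined as the percentage of enrolled participants who complete the combined intervention". Section 4.4.3 retains withdrawn participants' data but leaves their use to the investigator's discretion.

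**The concern.** A mandatory rule should give one answer for every eligible participant. This one does not. The same label has two meanings, one percentage rule reacts to the smallest possible change in people with almost no symptoms, and the visit at which the rules apply is missing from one of the two trials in the document.

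Three things are at stake. First, safety escalation: 11.3.3 points back to 5.2.3 for what counts as worsening that must reach the PI, so an unclear definition affects more than withdrawal. Second, the Aim 1 primary outcome: with 12 participants, a few rule-triggered losses would change the retention figure for reasons unrelated to whether people tolerate the intervention. Third, the data: neither 4.4.3 nor 8.1 says how participants withdrawn by rule enter the analysis.

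**Working it through.** The plan states no derived figure on this point, so there is none to reproduce. The check is an enumeration of every eligible integer baseline.

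**Inputs.** Highest eligible scores from 4.2: HAM-D 16, PANSS positive 34, YMRS 9. Triggers from 5.2.3: a 25% rise, a 25% rise, and a 7-point change. Assumptions: the reference is the baseline score, YMRS change means an increase, and PANSS positive scores start at 7 (the documents do not give the range).

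**Formula.** Smallest triggering score = 1.25 × baseline, rounded up, for HAM-D and PANSS positive; baseline + 7 for YMRS.

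| Scale | Rise needed | Triggers while still below the entry cut-off | Can reach the cut-off without a numeric trigger |
|---|---|---|---|
| HAM-D | 1 point at baseline 1–4; 2 at 5–8; 3 at 9–12; 4 at 13–16; undefined at 0 | baselines 1–12 | baselines 14–16 |
| PANSS positive | 2 points at 7–8, rising to 9 at 33–34 | baselines 7–27 | baselines 29–34 |
| YMRS | 7 points throughout | baselines 0–2 | baselines 4–9 |

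Worked cases:

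- HAM-D 4 to 5: 1/4 = 25%, so withdrawal is mandatory.
- HAM-D 16 to 19: 3/16 = 18.75%, no trigger, although 17 is exclusionary at entry. The trigger is 1.25 × 16 = 20.
- PANSS positive 34 to 42: 8/34 = 23.5%, no trigger, although 35 is exclusionary at entry. The trigger is 1.25 × 34 = 42.5, so 43.
- YMRS 0 to 7: current mania under 5.2.3, not under 4.2. YMRS 9 to 15: current mania under 4.2, but a change of 6 misses the numeric part of 5.2.3.
- The HAM-D and PANSS rules specify greater severity; the YMRS rule does not. Read literally, a 7-point fall would qualify.

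**Which participants the rules reach.** In Aim 1 the mid-point falls between the two periods. Group B (6 participants) has then had BrainHQ only, so a trigger removes the participant before any tDCS. With 12 enrolled, each such loss lowers retention by 1/12 = 8.3 percentage points. Group A has finished the tDCS block by then. If completing the combined intervention means finishing that block, a Group A trigger leaves retention unchanged; if it means finishing both periods, it also costs 8.3 points. In Aim 2 no visit bears the mid-point name. If the end-of-Week-4 visit is meant, the treatment period is over and only the follow-up can be lost.

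**Illustration of noise.** Suppose two HAM-D ratings with no true change differ by a normal amount with mean 0 and standard deviation SD. The chance of a trigger is 1 − Φ((rise needed − 0.5)/SD). SD = 2 (range 1.5 to 3) is an assumption.

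| Baseline HAM-D | Rise needed | SD 1.5 | SD 2 | SD 3 |
|---|---|---|---|---|
| 1–4 | 1 | 37% | 40% | 43% |
| 5–8 | 2 | 16% | 23% | 31% |
| 16 | 4 | 1% | 4% | 12% |

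**The case against.** The strongest reply is that entry criteria and worsening rules do different jobs. One selects on level; the other detects change. A participant may worsen while below an entry cut-off, or cross it by a small amount, without any contradiction. That stands. A reader might infer that 5.2.3 and 4.2 contradict each other in both directions on all three scales, but the direct textual conflict is confined to the two definitions of current mania. The 1-point case comes from applying a percentage to low scores, and it occurs on HAM-D only.

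A reader might also infer that participants who deteriorate past an entry level must stay in. The documents do not say so. Section 5.2.3 allows clinical observation of mania, its list is open-ended, and it requires close monitoring of mood; 4.4.2 lets the investigator withdraw anyone at unacceptable risk. What remains is narrower: for depression and psychosis in that range, the numeric rule is silent and only clinical discretion applies.

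A third tempting reading is that rating noise will remove participants during Aim 2 treatment. The score rules are tied to a visit that Aim 2 lacks, so this is unsupported. Nor does every Aim 1 trigger clearly cost 8.3 points.

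Finally, the noise model holds SD constant and ignores the floor of the scale at zero, and the documents give no distribution of baseline HAM-D. The objection is right that 40% is not an expected rate for this trial.

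On data handling, 5.2.4 already seeks outcome assessments at early termination and 4.4.3 keeps the data. Neither commits the analysis to using them.

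**Conclusion.** The point holds in limited form, as something the sponsor should correct. Three defects follow from the text and arithmetic: two definitions of current mania, one without a direction; a HAM-D rule that fires on 1 point at baselines 1 to 4 and has no value at 0, while rises such as HAM-D 16 to 19 or PANSS positive 34 to 42 meet no numeric trigger; and a mid-point visit that exists only in Aim 1. The first two rest on baseline being the reference score.

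The effect on the Aim 1 primary outcome is 8.3 percentage points for each Group B trigger, assuming 12 enrolled, and depends on the reading of completion for Group A. The roughly 40% false-trigger chance at HAM-D baselines 1 to 4 (37% to 43% over the assumed SD range) shows only how sensitive the rule is there. How many participants will have such baselines is unknown. For Aim 2 the documents support a gap in the rule, not a predicted loss of participants during treatment.

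**What to change.** Amend the protocol so that 3.4, 4.2, 5.2.3, 5.4 and 5.5 agree on three matters:

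1. One definition of current mania, or two separate labels if two concepts are intended, with the direction of the YMRS change and the reference score stated.
2. How the percentage rules work at low baselines and at zero, and whether the region above the entry cut-off but below the numeric trigger is deliberately left to clinical judgement.
3. The visit at which the score rules apply in each aim.

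All thresholds are for the investigators and the IRB; none is proposed here.

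On the analysis side, define completion of the combined intervention for each Aim 1 sequence, and report rule-triggered withdrawals separately from voluntary drop-out beside the retention figure. In 4.4.3, replace discretionary use with a commitment to keep all available data from withdrawn participants, including early-termination assessments, in the as-randomised Aim 2 comparison.

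The cost is amendment wording and one extra line in the retention table.

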5.2.4 Early Termination Assessments

If early termination occurs and, if the participant is willing and able, all of the outcomes and safety assessments noted above for the final experimental visit will be performed.

5.3 Computerized cognitive training

Participants will be provided a personalized login to the BrainHQ website and provided a tutorial to orient them to the training program. They will complete a total of 10 hours of working memory exercises specifically, as selected and monitored by the study team. BrainHQ can be accessed online on a desktop computer, laptop, Apple tablet, or Apple mobile phone. In the event that a participant does not have reliable access to one of these devices, arrangements will be made to complete training on an available computer at RUB.

5.4 Subsequent assessment visits (post-treatment and follow-up)

Participants will complete follow-up assessments at the conclusion of treatment (post-treatment) and at one-month follow-up. Measures will include:

1. Hamilton Depression Rating Scale (HAM-D)
2. Young Mania Rating Scale (YMRS)
3. Positive and Negative Syndrome Scale (PANSS)
4. MCCB: Trails A, letter-number span, spatial span
5. Trails B
6. Specific Levels of Functioning (SLOF) clinician-rated questionnaire

These visits are expected to last up to 1.5 hours.

5.5 Assessments

Participants will complete assessments at three time points: baseline (pre-treatment), post-treatment, and follow-up.

Assessment schedule and administration time requirements.

	Baseline	Post-treatment	Follow-up	Administration time (mins)
Clinical measures				
MINI diagnostic interview	x			60
HAM-D, YMRS, PANSS	x	x	x	15-30
C-SSRS	x			5
Neuropsychological measures				
WRAT reading	x			5
MCCB (Trails A*; letter-number span; spatial span)	x	x	x	30
Trails B*	x	x	x	5
Functional measures				
SLOF	x	x	x	10
Total estimated time	≤ 2.5 hours	≤ 1.5 hours	≤ 1.5 hours	

*Trails A and B will be administered as non-working memory neurocognitive comparison measures

5.5.1 Assessment of Suicidality

For any potential participant who reports concerning suicidal thoughts/behaviors (defined according to the MINI, HAM-D, or C-SSRS), the PI will be notified and a further risk assessment of the patient will be conducted, including the identification of risk factors (e.g., substance abuse, active psychosis, hopelessness), mitigating factors (e.g., social support, degree of control over suicidal thoughts, religious beliefs against suicide) and the level of suicidal ideation/behavior. An intervention plan will be formulated, taking into account the level of risk and treatment resources available to the potential participant. This could include monitoring by family, contact with a treating clinician (with the patient's permission), follow-up phone calls, or urgent evaluation in the psychiatric emergency room. For individuals without a treating clinician, referrals to available community resources will be made.

